### 7.3. *Additional Measurements*

Additional measurements based on the VARC endpoints and definitions (see references and Table 26.2-1 in the Appendix for definitions) will be collected peri- and post-procedure, at discharge or 7 days post-procedure (whichever comes first), 30 days, 3 months, 6 months, and 1, 2, 3, 4, and 5 years post index procedure, unless otherwise specified below. Data will be evaluated on an ITT basis.

- Safety endpoints adjudicated by an independent Clinical Events Committee (CEC):
  - Mortality: all-cause, cardiovascular, and non-cardiovascular
  - Stroke: disabling and non-disabling
  - Composite of all-cause mortality and disabling stroke
  - Myocardial infarction (MI): periprocedural  $\leq 72$  hours post index procedure) and spontaneous ( $>72$  hours post index procedure)

- Bleeding: life-threatening (or disabling) and major
- Acute kidney injury ( $\leq 7$  days post index procedure): based on AKIN System Stage 3 (including renal replacement therapy) or Stage 2
- Major vascular complication
- Repeat procedure for valve-related dysfunction (surgical or interventional therapy)
- Hospitalization for valve-related symptoms or worsening congestive heart failure (NYHA class III or IV)
- New permanent pacemaker implantation resulting from new or worsened conduction disturbances (including left bundle branch block [LBBB] and third degree atrioventricular block)
- New onset of atrial fibrillation and atrial flutter
- Coronary obstruction (periprocedural)
- Ventricular septal perforation (periprocedural)
- Mitral apparatus damage (periprocedural)
- Cardiac tamponade (periprocedural)
- Prosthetic aortic valve malapposition, including valve migration, valve embolization, ectopic valve deployment, or transcatheter aortic valve (TAV)-in-TAV deployment
- Prosthetic aortic valve thrombosis
- Prosthetic aortic valve endocarditis
- Prosthetic aortic valve performance as measured by transthoracic echocardiography (TTE) and assessed by an independent core laboratory, including effective orifice area, mean and peak aortic gradients, peak aortic velocity, and grade of aortic regurgitation
- Functional status as evaluated by the following:
  - 5-m gait speed test (at 1 year compared to baseline)
  - New York Heart Association (NYHA) classification
- Neurological status as determined by the following:
  - National Institutes of Health Stroke Scale (NIHSS) at discharge and 1 year

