EC16.	Subject has any therapeutic invasive cardiac procedure (including balloon aortic valvuloplasty) within 30 days prior to the index procedure (except for pacemaker implantation which is allowed).
EC17.	Subject has untreated coronary artery disease, which in the opinion of the treating physician, is clinically significant and requires revascularization.
EC18.	Subject has documented left ventricular ejection fraction <30%.
EC19.	Subject is in cardiogenic shock or has hemodynamic instability requiring inotropic support or mechanical support devices.
EC20.	Subject has severe peripheral vascular disease (including aneurysm defined as maximal luminal diameter >5 cm or with documented presence of thrombus, marked tortuosity, narrowing of the abdominal aorta, severe unfolding of the thoracic aorta or thick [>5 mm] protruding or ulcerated atheroma in the aortic arch) or symptomatic carotid or vertebral disease.
EC21.	Femoral artery lumen of <6.0 mm for subjects requiring 23 mm valve size or <6.5 mm for subjects requiring 27 mm valve size, or severe iliofemoral tortuosity or calcification that would prevent safe placement of the introducer sheath.
EC22.	Current problems with substance abuse (e.g., alcohol, etc.).

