**Table 11.1-1: Study Event Schedule – Main Trial Cohort**

Assessment	Screening a	Baseline b	Procedure	Within 1 Day Post-procedure	Prior to Discharge or 7 Days Post-Procedure	30 Days c (±7 Days) Office Visit	3 Months c (±14 Days) Office Visit	6 Months c (±30 Days) Office Visit	12 Months c (±45 Days) Office Visit	24–60 Months c [Annual] (±45 Days) Office Visit
------------	------------------------	-----------------------	-----------	-----------------------------	---	---	---	---	--	--

q: QOL survey at 36 and 60 months.

r: Procedural cine-angiogram including the final post-deployment aortogram of the ascending aorta should be sent to the CT/X-Ray Core Laboratory for analysis.

s: AEs and ADEs will be monitored and collected from the time of enrollment through 12-month follow-up. For subjects who do not receive the study device, AEs will be monitored through 30-day follow-up.

t: Device deficiencies (for the Lotus Valve System), SAEs, SADEs, USADEs, and CEC events will be monitored and reported to Boston Scientific for all enrolled subjects from the time of enrollment through termination of the study. For subjects who do not receive the study device, the mentioned events will be monitored through 30 days post-index procedure. Please refer to Section 7.3 for a list of CEC events and Table 26.2-1 for definitions of these events, which specify data required for CEC adjudication.

Abbreviations: AE=adverse event; ADE=adverse device effect; AKI=acute kidney injury; CBC=complete blood count; CEC=Clinical Events Committee; CK-MB=creatinine kinase-myoglobin band; CRC=Case Review Committee; CT=computed tomography; ECG=electrocardiogram; LDH=lactate dehydrogenase; LV=left ventricle; MRI=magnetic resonance imaging; mRS=modified Rankin Scale; NIHSS=National Institutes of Health Stroke Scale; NYHA=New York Heart Association; QOL=Quality of Life; SAE=serious adverse event; SADE=serious adverse device effect; STS=Society of Thoracic Surgery; TEE=transesophageal Doppler echocardiography; TTE=transthoracic Doppler echocardiography; USADE=unanticipated serious adverse device effect

[figure not shown]

Figure 11.1-2: REPRISE II Study Design – Extended Trial Cohort

Table 11.1-2: Study Event Schedule – Extended Trial Cohort

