#### 12.2.1. Analysis Sets

The primary analysis population for the primary device performance endpoint will be the subject population implanted with the Lotus Valve (as-treated subject population).

The primary safety endpoint will be evaluated on an ITT basis (all subjects enrolled, whether or not a study device is implanted). For the ITT analysis, all subjects who sign the written ICF and are enrolled in the study will be included in the analysis sample, regardless of whether the study device was implanted.

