#### **13.3.3. Electrocardiography (ECG) Core Laboratory**

All 12-lead ECGs performed at each of the required protocol visits will be sent to an ECG core laboratory (see study Manual of Operations) for independent analyses. These analyses will minimize bias and will provide consistent interpretation of the ECGs.

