**Table 26.2-1: Definitions**

[figure not shown]
Term	Definition

AORTIC DISSECTION
	
Intimal tear resulting in blood splitting the aortic media and producing a false lumen that can progress in an antegrade or retrograde direction Aortic dissection is further classified using Stanford classification (Types A and B depending on whether ascending or descending aorta involved) or DeBakey classification (Types I, II and III) [see Figure below].
 

AORTIC REGURGITATION (AR)
	
The leaking of the aortic valve that causes blood to flow in the reverse direction during ventricular diastole, from the aorta into the left ventricle.
 
The echocardiographic findings in severe aortic regurgitation include the following.
 
 
• An AR color jet dimension >60% of the left ventricular outflow tract diameter (may not be true if the jet is eccentric)
 
• The pressure half-time of the regurgitant jet is <250 msec
 
• Early termination of the mitral inflow (due to increase in LV pressure due to the AR)
 
• Early diastolic flow reversal in the descending aorta.
 
• Regurgitant volume >60 mL
 
• Regurgitant fraction >55%
 

ARRHYTHMIA
	
Any variation from the normal rhythm of the heartbeat, including sinus arrhythmia, premature beat, heart block, atrial fibrillation, atrial flutter and tachycardia. Complete heart block, ventricular tachycardia and ventricular fibrillation are considered major arrhythmias. Data should be collected on any new arrhythmia resulting in hemodynamic instability or requiring therapy (therapy includes electrical/medical cardioversion or initiation of a new medication [oral anticoagulation, rhythm or rate controlling therapy]).
 
New onset atrial fibrillation or atrial flutter (AF) is diagnosed as any arrhythmia within hospitalization that has the ECG characteristics of AF and lasts sufficiently long to be recorded on a 12-lead ECG, or at least 30 seconds on a rhythm strip.
 
The therapeutic approach to new-onset AF (spontaneous conversion, electrical or medical cardioversion, initiation of oral anticoagulation, and rate or rhythm control medications) and any clinical consequences should be documented.
 
Note: See also definitions for conductance disturbance and permanent pacemaker.

BLEEDING
	
Life-threatening or Disabling Bleeding

Table 26.2-1: Definitions

Term	Definition

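### New-onset AF is defined in-hospital with no AF-free baseline yet reported to 5 years; an all-enrolled new-pacemaker rate is diluted by subjects already paced

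*Combined protocol and SAP*

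**What the plan says.** **AF definition.** The arrhythmia entry of Table 26.2-1 reads: "New onset atrial fibrillation or atrial flutter (AF) is diagnosed as any arrhythmia within hospitalization that has the ECG characteristics of AF". The rhythm must also be captured on a 12-lead ECG or last at least 30 seconds on a strip. The entry does not say which hospital stay is meant, and it does not require that the subject was free of AF beforehand.

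**AF reporting.** Section 7.3 lists "New onset of atrial fibrillation and atrial flutter" among the safety endpoints adjudicated by the Clinical Events Committee (CEC). Collection includes "30 days, 3 months, 6 months, and 1, 2, 3, 4, and 5 years post index procedure, unless otherwise specified below". The AF item carries no limit of its own. Other items in the list do: acute kidney injury stops at 7 days, and coronary obstruction, septal perforation, mitral damage and tamponade are marked periprocedural. A footnote to Table 11.1-1, repeated under Table 11.1-2, says "CEC events will be monitored and reported to Boston Scientific for all enrolled subjects from the time of enrollment through termination of the study" (30 days if no valve is implanted) and points to Table 26.2-1 for the event definitions.

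**ECGs.** Both schedules require a 12-lead ECG at the 30-day, 3-, 6- and 12-month office visits and none at 24–60 months. Section 13.3.3 adds: "All 12-lead ECGs performed at each of the required protocol visits will be sent to an ECG core laboratory".

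**Denominator.** For all additional measurements section 7.3 says "Data will be evaluated on an ITT basis". Section 12.2.1 explains the ITT analysis, in the context of the primary safety endpoint: "all subjects who sign the written ICF and are enrolled in the study will be included in the analysis sample", implanted or not.

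**Entry.** EC16 bars recent invasive cardiac treatment, "except for pacemaker implantation which is allowed". EC24 excludes only an untreated conduction disorder that needs a pacemaker. AF does not appear among EC1–EC24, and EC11 admits subjects on chronic anticoagulation if they tolerate an antiplatelet agent.

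**The concern.** There are two separate problems.

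First, the AF endpoint has one time frame in the list of measurements and another in the definition that the CEC is told to use. The trial will hold centrally read ECGs from four scheduled office visits, but AF found there in a subject who is not in hospital does not meet the written definition. Late AF counts would then depend on whether a subject happened to be admitted. The definition also leaves open whether AF present before the procedure, and still present during the stay, is an event.

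Second, a subject who already has a pacemaker is essentially not at risk of receiving a new one. If such subjects stay in the denominator, the new-pacemaker rate falls below the risk faced by a patient without one.

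At stake is how two descriptive safety rates of a valve trial can be read, not the outcome of either hypothesis test.

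**Working it through.** The plan gives no AF rate, pacemaker rate or baseline prevalence, so there is no figure to reproduce. The check sets the sections side by side and then uses a simple identity with assumed values.

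**Step 1: time frame of AF**

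| Setting in which AF is first seen | Within the reporting period of 7.3? | Meets Table 26.2-1? |
|---|---|---|
| Index hospital stay | Yes | Yes |
| Later admission | Yes | Yes, since the stay is not limited to the index one |
| Office-visit ECG at 30 days or 3, 6 or 12 months, subject not admitted | Yes | No |
| Known before the procedure and present in hospital | It should not count as new | Yes, if read literally |

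The third row can lower the rate and the fourth can raise it.

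**Step 2: the identity**

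Let q be the share of enrolled subjects with the condition at baseline, r the risk of a new event in subjects free of it, and s the chance that a subject with the condition at baseline is counted as an event.

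- Rate over all enrolled = r(1 − q) + qs
- Rate among subjects free of the condition = r

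**Step 3: pacemaker**

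Take s = 0, because a subject already paced is essentially not a candidate for a new device. The all-enrolled rate is then r(1 − q), and the relative shortfall is q. With assumed r = 30% and the planned 250 subjects (120 + 130):

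- q = 10%: 225 at risk; 0.30 × 0.90 = 0.27, so 27% is reported.
- q = 20%: 200 at risk; 0.30 × 0.80 = 0.24, so 24% is reported.

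The Kaplan-Meier estimates named in section 12.1.2 do not remove the shortfall, because subjects already paced stay in the risk set unless it is defined to leave them out.

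**Step 4: direction for AF**

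The all-enrolled AF rate is below r if s < r and above r if s > r. Assumed q = 30% and r = 10% serve only to show the change of sign:

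- s = 0: 0.10 × 0.70 = 0.07
- s = 0.5: 0.07 + 0.30 × 0.5 = 0.22
- s = 1: 0.07 + 0.30 × 1 = 0.37

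The documents do not determine s. Step 4 also leaves out the loss of AF first seen at an office visit, which acts downward. These figures are therefore not an estimate of the bias.

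**The case against.** **An ITT basis need not mean an all-enrolled denominator for every item.** Section 7.2 puts successful repositioning and successful retrieval on the same ITT basis, although each applies only if the manoeuvre was attempted. The wording can therefore coexist with conditional denominators. Section 12.2 also refers to a study-specific statistical analysis plan; the text supplied contains no at-risk rule, but such a plan might set one. This stands in part: the dilution follows if sections 7.3 and 12.2.1 are applied as written, and what is certain is that no at-risk set is given for either new event.

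**The committee would not call known AF new.** This is plausible, because the name of the endpoint implies it. The definition does not say so, however, and a rule left to judgement is what a written definition should replace.

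**Post-discharge AF is not all lost.** This is correct. AF during a readmission can qualify. Table 26.2-1 also asks for data on any new arrhythmia that causes instability or needs therapy, adverse events are collected to 12 months, and office-visit ECGs go to the core laboratory. The gap is narrower: AF first seen on an outpatient ECG is recorded but does not meet the endpoint definition.

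**The consequence is small.** This also stands. Section 12.1.2 plans no inference on the additional endpoints, and an all-enrolled incidence is a legitimate descriptive figure if it is labelled as such.

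**Conclusion.** The point holds in a limited form, as a minor correction.

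- **AF:** Section 7.3 and Table 26.2-1 conflict on the time frame, and no AF-free baseline is required. The reported rate is therefore unreliable, in a direction the documents do not fix.
- **Pacemaker:** If the rate is taken over all enrolled subjects, it is understated whenever any enrolled subject is already paced, by a relative amount equal to the baseline prevalence. The illustration of 30% becoming 27–24% rests on an assumed prevalence of 10–20% and on subjects already paced never being counted. EC16 shows that pacemakers are permitted at entry, not how common they are.

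A reader might infer that both rates are understated. That is not shown for AF, because counting pre-existing AF would push its rate up. Nor do the documents support the view that every late AF rate is wrong by definition, since readmission AF can qualify. A reader might also infer that comparisons with other studies would favour this device. No such comparison of AF or pacemaker rates is specified, Table 4.1-1 has no column for either, and the denominators used elsewhere are not given.

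Neither primary endpoint is affected.

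**What to change.** 1. Give AF one time frame. Either extend the Table 26.2-1 definition to AF on any protocol or clinical ECG after the index procedure, or limit the item in section 7.3 (and the matching synopsis entry) to hospitalization, stating whether that means the index stay or any stay. If the wider definition is chosen, note that no ECG is scheduled after 12 months, so later AF would come only from clinical ECGs.
2. State in Table 26.2-1 that an event is new only if the subject had no AF, or no pacemaker, at baseline, judged from the cardiac history and the pre-procedure ECG.
3. Report both rates among enrolled subjects free of the condition at baseline, with that denominator shown, beside the ITT rate. Define the Kaplan-Meier risk set in the same way.

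The cost is a few lines of definition text and an added column in the table shells. The screening history and the ECG sent to the core laboratory (sections 11.4 and 11.5) are already collected. The wider AF definition would add some CEC review of office-visit ECGs that show AF.

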**Table 26.2-1: Definitions**

Term	Definition
	
a primary focus -OR-
 
 
○ Microorganisms consistent with infective endocarditis from persistently positive blood cultures defined as noted below.                             
 
▪ Two (2) positive cultures of blood samples drawn >12 hours apart -OR-
 
▪ All of 3 or a majority of 4 separate cultures of blood (with first and last sample drawn 1 hour apart)
 
 
 
● Evidence of endocardial involvement                             
 
○ Positive echocardiogram for infective endocarditis defined as noted below.                                     
 
▪ Oscillating intracardiac mass on valve or supporting structures, in the path of regurgitant jets, or on implanted material in the absence of an alternative anatomic explanation -OR-
 
▪ Abscess -OR-
 
▪ New partial dehiscence of prosthetic valve
 
 
 
-OR-
 
○ New valvular regurgitation (worsening or changing of preexisting murmur not sufficient)
 
 
 
 
Minor Criteria
 
 
● Predisposition: predisposing heart condition or intravenous drug use
 
● Fever: temperature >38.0° C (100.4° F)
 
● Vascular phenomena: major arterial emboli, septic pulmonary infarcts, mycotic aneurysm, intracranial hemorrhage, conjunctival hemorrhages, and Janeway lesions
 
● Immunologic phenomena: glomerulonephritis, Osler's nodes, Roth spots, and rheumatoid factor
 
● Microbiological evidence: positive blood culture but does not meet a major criterion as noted above or serological evidence of active infection with organism consistent with infective endocarditis
 
● Echocardiographic findings: consistent with infective endocarditis but do not meet a major criterion as noted above
 
 
Implanted valve endocarditis includes any infection involving an implanted valve. The diagnosis of operated valvular endocarditis is based on one of the following criteria.
 
 
● Fulfillment of the Duke endocarditis criteria as defined above
 
● Evidence of abscess, paravalvular leak, pus, or vegetation confirmed as secondary to infection by histological or bacteriologic studies during a re-operation
 
● Findings of abscess, pus, or vegetation involving a repaired or replaced valve during an autopsy.
 

EXPLANT	Removal of the investigational valve implant for any reason.
FRAILITY	Slowness, weakness, exhaustion, wasting and malnutrition, poor endurance and inactivity, loss of independence.
HEMOLYSIS	Two plasma free hemoglobin values >40 mg/dL with the two readings taken within a single 48-hour period. If the second plasma free hemoglobin assessment is not performed within 48 hours following an initial determination of >40 mg/dL, this would qualify as an AE.
HOSTILE CHEST	Any of the following or other reasons that make redo operation through sternotomy or right anterior thoracotomy prohibitively hazardous:

**Table 26.2-1: Definitions**

Term	Definition
	
 
Abnormal chest wall anatomy due to severe kyphoscoliosis or other skeletal abnormalities (including thoracoplasty, Potts' disease)
 
Complications from prior surgery
 
Evidence of severe radiation damage (e.g. skin burns, bone destruction, muscle loss, lung fibrosis or esophageal stricture)
 
History of multiple recurrent pleural effusions causing internal adhesions
 

INTERNAL MAMMARY ARTERY OR OTHER CRITICAL CONDUIT(S) CROSSING MIDLINE AND/OR ADHERENT TO POSTERIOR TABLE OF STERNUM
	
A patent IMA graft that is adherent to the sternum such that injuring it during reoperation is likely. A patient may be considered extreme risk if any of the following are present:
 
 
The conduit(s) are radiographically indistinguishable from the posterior table of the sternum.
 
The conduit(s) are radiographically distinguishable from the posterior table of the sternum but lie within 2-3mm of the posterior table.
 

INTRACRANIAL HEMORRHAGE
	
Collection of blood between the brain and skull; subcategorized as epidural, subdural, and subarachnoid bleeds.

LEFT BUNDLE BRANCH BLOCK (LBBB)
	
The appearance of typical complete LBBB in the three KEY leads (I, V1, and V6) with the following diagnostic criteria [see Figure below].
 
 
The heart rhythm must be supraventricular in origin
 
QRS widening to at least 0.12 sec
 
An upright (monophasic) QRS complex in leads I and V6; the QRS may be notched, but there should not be any q wave in either lead I or lead V6.
 
A predominantly negative QRS complex in lead V1; there may or may not be an initial small r wave in lead V1, that is, lead V1 may show either a QS or RS complex.
 
  
The figure is a 3x4 grid of ECG leads. The top row shows leads I, aVR, V1, and V4. The middle row shows leads II, aVL, V2, and V5. The bottom row shows leads III, aVF, V3, and V6. Lead I shows a tall, narrow, upright QRS complex. Lead V1 shows a deep, narrow, negative QRS complex. Lead V6 shows a tall, narrow, upright QRS complex. The other leads are shaded out.


LIVER DISEASE (SEVERE) /CIRRHOSIS
	
Any of the following:
 
 
Child-Pugh class C
 
MELD score <math>\geq 10</math>
 
Portal-caval, spleno-renal, or transjugular intrahepatic portal shunt
 
Biopsy proven cirrhosis with portal hypertension or hepatocellular dysfunction
 

MITRAL VALVE APPARATUS DAMAGE
	
Angiographic or echocardiographic evidence of a new damage to the mitral valve apparatus (chordae papillary muscle, or leaflet) during or after the TAVR procedure.

MYOCARDIAL
	
Periprocedural MI (<math>\leq 72</math> hours after the index procedure)

**Table 26.2-1: Definitions**

Term	Definition								
INFARCTION (MI)	
 
• New ischemic symptoms (e.g., chest pain or shortness of breath) or new ischemic signs (e.g., ventricular arrhythmias, new or worsening heart failure, new ST-segment changes, hemodynamic instability, new pathological Q waves in at least two contiguous leads, or imaging evidence of new loss of viable myocardium or new wall motion abnormality)
 
-AND-
 
• Elevated cardiac biomarkers (preferably CK-MB) within 72 h after the index procedure, consisting of at least one sample post-procedure with a peak value exceeding 15× upper reference limit (troponin) or 5× for CK-MB. If cardiac biomarkers are increased at baseline (>99th percentile), a further increase of at least 50% post-procedure is required AND the peak value must exceed the previously stated limit.
 
 
Spontaneous MI (>72 hours after the index procedure) Any one of the following criteria applies.
 
 
• Detection of rise and/or fall of cardiac biomarkers (preferably troponin) with at least one value above the 99th percentile URL, together with evidence of myocardial ischemia with at least one of the following               
 
○ Symptoms of ischemia
 
○ ECG changes indicative of new ischemia [new ST-T changes or new LBBB]
 
○ New pathological Q waves in at least two contiguous leads
 
○ Imaging evidence of new loss of viable myocardium or new wall motion abnormality
 
 
 
• Sudden, unexpected cardiac death, involving cardiac arrest, often with symptoms suggestive of myocardial ischemia, and accompanied by presumably new ST-segment elevation, or new LBBB, and/or evidence of fresh thrombus by coronary angiography and/ or at autopsy, but death occurring before blood samples could be obtained, or at a time before the appearance of cardiac biomarkers in the blood.
 
• Pathological findings of an acute myocardial infarction.
 
								
NEUROLOGICAL EVENT	Any central, new neurological deficit, whether temporary or permanent and whether focal or global, that occurs after the subject emerges from anesthesia								
NEW YORK HEART ASSOCIATION CLASSIFICATION (NYHA)	Classification system for defining cardiac disease and related functional limitations into four broad categorizations: 
  
 Class I	Subject with cardiac disease but without resulting limitations of physical activity. Ordinary physical activity does not cause undue fatigue, palpitation, dyspnea, or anginal pain.	
 
 Class II	Subjects with cardiac disease resulting in slight limitation of physical activity. They are comfortable at rest. Ordinary physical activity results in fatigue, palpitation, dyspnea, or anginal pain.	
 
 Class III	Subjects with cardiac disease resulting in marked limitation of physical activity. They are comfortable at rest. Less than ordinary physical activity causes fatigue, palpitation, dyspnea, or anginal pain.	
 
 Class IV	Subjects with cardiac disease resulting in inability to carry on any physical activity without discomfort. Symptoms of cardiac insufficiency or of the anginal syndrome may be present even at rest. If any physical activity is undertaken, discomfort is increased.	
  
	Class I	Subject with cardiac disease but without resulting limitations of physical activity. Ordinary physical activity does not cause undue fatigue, palpitation, dyspnea, or anginal pain.	Class II	Subjects with cardiac disease resulting in slight limitation of physical activity. They are comfortable at rest. Ordinary physical activity results in fatigue, palpitation, dyspnea, or anginal pain.	Class III	Subjects with cardiac disease resulting in marked limitation of physical activity. They are comfortable at rest. Less than ordinary physical activity causes fatigue, palpitation, dyspnea, or anginal pain.	Class IV	Subjects with cardiac disease resulting in inability to carry on any physical activity without discomfort. Symptoms of cardiac insufficiency or of the anginal syndrome may be present even at rest. If any physical activity is undertaken, discomfort is increased.
Class I	Subject with cardiac disease but without resulting limitations of physical activity. Ordinary physical activity does not cause undue fatigue, palpitation, dyspnea, or anginal pain.								
Class II	Subjects with cardiac disease resulting in slight limitation of physical activity. They are comfortable at rest. Ordinary physical activity results in fatigue, palpitation, dyspnea, or anginal pain.								
Class III	Subjects with cardiac disease resulting in marked limitation of physical activity. They are comfortable at rest. Less than ordinary physical activity causes fatigue, palpitation, dyspnea, or anginal pain.								
Class IV	Subjects with cardiac disease resulting in inability to carry on any physical activity without discomfort. Symptoms of cardiac insufficiency or of the anginal syndrome may be present even at rest. If any physical activity is undertaken, discomfort is increased.								
NONSTRUCTURAL	Any abnormality not intrinsic to the valve itself that results in stenosis or regurgitation of the operated valve or hemolysis. The term nonstructural dysfunction								

Table 26.2-1: Definitions

Term	Definition
DYSFUNCTION	
refers to problems (exclusive of thrombosis and infection) that do not directly involve valve components yet result in dysfunction of an operated valve, as diagnosed by re-operation, autopsy, or clinical investigation. Nonstructural dysfunction includes the following.
 
 
• Entrapment by pannus, tissue, or suture
 
• Paravalvular leak
 
• Inappropriate sizing or positioning
 
• Residual leak or obstruction after valve implantation or repair
 
• Clinically important intravascular hemolytic anemia
 
• Development of aortic or pulmonic regurgitation as a result of technical errors
 
• Dilatation of the sinotubular junction
 
• Dilatation of the valve annulus after either valve replacement with stentless prostheses, new onset of coronary ischemia from coronary ostial obstruction, or paravalvular aortic regurgitation
 

PARAVALVULAR REGURGITATION	
Leakage due to a separation of the prosthetic valve from the annulus. Any evidence of leakage of blood around the device. Diagnosis of paravalvular regurgitation may be obtained from TEE/TTE, however, definitive diagnosis is obtained at re-operation, explant, or autopsy.

PERMANENT PACEMAKER (PPM) IMPLANTATION	
Implantation of new PPM after the index procedure resulting from new or worsened conduction disturbances (including new left bundle branch block [LBBB] and third degree atrioventricular block)
 
 
• Procedure-related: PPM is implanted in subjects with new onset or worsened conduction disturbances occurring post index procedure
 
• Not related to procedure: PPM is implanted in subjects with known conduction disturbances that did not advance after the index procedure.
 
 
Note: See also definitions for arrhythmia and conductance disturbance.

PORCELAIN AORTA	
Heavy circumferential calcification of the entire ascending aorta extending to the arch such that aortic cross-clamping is not feasible

PROCEDURE RELATED COMPLICATIONS	
Complications associated with any part of the vascular access procedure, associated treatments or necessary secondary interventions that do not necessarily involve the device. This includes morbidity associated with either pre-medication, or anesthesia, or other adjunct to the surgical procedure. Other technical errors including inappropriate subject selection, inappropriate operator techniques, measurements, or judgment that do not involve the device itself are also included.

PROCEDURE-RELATED EVENTS	
Events occurring during or as a direct result of the index procedure.

REPEAT PROCEDURE FOR VALVE-RELATED DYSFUNCTION	
Any surgical or percutaneous interventional catheter procedure that repairs, otherwise alters or adjusts, or replaces a previously implanted valve. In addition to surgical re-operations, enzymatic, balloon dilatation, interventional manipulation, repositioning, or retrieval, and other catheter-based interventions for valve-related complications are also considered reinterventions. Cardiac reinterventions will be categorized as repeat TAVR, valvuloplasty, or surgical AVR.
 
 
• Conversion to open surgery
 
• Conversion to open sternotomy during the TAVR procedure secondary to any procedure-related complications.
 
• Unplanned use of CPB
 
• Unplanned use of CPB for hemodynamic support at any time during the TAVR
 

Table 26.2-1: Definitions

Term	Definition
	procedure.
RESPIRATORY INSUFFICIENCY	Inadequate ventilation or oxygenation
RESPIRATORY FAILURE	The need for ventilatory support for >72 hours associated with an inability to wean from the respirator for any reason.
RIGHT VENTRICULAR INSUFFICIENCY	
 
• Defined as sequelae of right ventricular failure including the following. 
 
○ Significantly decreased right ventricular systolic and/or diastolic function
 
○ Tricuspid valvular regurgitation secondary to elevated pressure
 
 
 
• Clinical symptoms to include the following. 
 
○ Hepatic congestion
 
○ Ascites
 
○ Anasarca
 
○ Presence of “hepato-jugular reflux”
 
○ Edema
 
 
 
 
Severe right ventricular dysfunction or severe pulmonary hypertension is primary or secondary pulmonary hypertension with PA systolic pressures greater than 2/3 of systemic pressure.

SERIOUS ADVERSE EVENT (SAE)	
Adverse event that resulted in the following.
 
 
• Led to a death
 
• Led to serious deterioration in the health of the subject, that resulted in one or more of the following. 
 
○ Life-threatening illness or injury
 
○ Permanent impairment of a body structure or a body function
 
○ In-patient or prolonged hospitalization
 
○ Medical or surgical intervention to prevent life- threatening illness or injury or permanent impairment to a body structure or a body function,
 
 
 
• Led to fetal distress, fetal death or a congenital abnormality or birth defect
 
 
Note 1: Planned hospitalization for a pre-existing condition, or a procedure required by the protocol, without serious deterioration in health, is not considered a serious adverse event.

SERIOUS ADVERSE DEVICE EFFECT (SADE)	Adverse device effect that has resulted in any of the consequences characteristic of a serious adverse event
SOURCE DATA (per ISO 14155:2011)	All information in original records of clinical findings, observations, or other activities in a clinical investigation, necessary for the reconstruction and evaluation of the clinical investigation
SOURCE DOCUMENT (per ISO 14155:2011)	Printed, optical or electronic document containing source data. Examples: Hospital records, laboratory notes, device accountability records, photographic negatives, radiographs, records kept at the investigation center, at the laboratories and at the medico-technical departments involved in the clinical investigation.
STROKE 	
Stroke is defined as an acute episode of focal or global neurological dysfunction caused by brain, spinal cord, or retinal vascular injury as a result of hemorrhage or infarction
 
Stroke Classification
 
 
• Ischemic Stroke is defined as an acute episode of focal cerebral, spinal, or retinal dysfunction caused by an infarction of central nervous system tissue.
 

